Title Page

Official title: Clinical Study Protocol

NCT number: NCT04399005

Date: May 21, 2020

Protocol

Study title: Effectiveness between daily and after-each-case room disinfection of the endoscopy unit during the COVID-19 pandemic.

Approval date: May 21, 2020

Affiliation: The First Affiliated Hospital of Zhejiang Chinese Medical University.

Study description:

Brief Summary: The aim of our study was to evaluate the difference of effectiveness between daily and after-each-case room disinfection in the endoscopy unit during the COVID-19 pandemic.

Detailed Description: This study divided into two groups: daily and after-each-case room disinfection groups. Each group was again subdivided into sedation and non-sedation gastroscopy, and with or without ventilation operation room.

Samples were collected as follows: for air sample of the operation unit, a six-stage sieve percussion air sampler (airflow rate: 28.3L/min; sampling time, 4 min) was used; for workstation mouse, a sterile cotton was used to wipe the surface of the mouse; and for the isolation gown of the endoscopist, control panel buttons, and bed headboard of the patient, a contact plate was used.

Study Time:

Start: May 25, 2020

Primary Completion: June 5, 2020

Study Completion: June 10, 2020

Eligibility criteria:

Inclusion Criteria: All the cases received gastroscopy.

Exclusion Criteria: High-risk personal through epidemiological history, symptoms, body temperature, COVID-19 virus nucleic acid test, and chest computed tomography scan.

Arms and Interventions:

Arms:

Daily room disinfection: The room disinfection after completing eight non-sedation gastroscopies or four sedation gastroscopies.

After-each-case room disinfection: The room disinfection performed after completing the examination of each patient.

Assigned Interventions:

Daily room disinfection: The room disinfection after completing eight non-sedation gastroscopies or four sedation gastroscopies (Room disinfection: Room disinfection was defined as cleansing and disinfection of the surface of the facility, endoscopist's isolation gown, and air in the endoscopy room after the examination. Specifically, sanitizing wipes containing quaternary ammonium salt, alcohol, and interfacial activator were used to wipe the surfaces and the air disinfection machine was switched on for 30 min continuously).

After-each-case room disinfection: The room disinfection performed after completing the examination of each patient (Room disinfection: Room disinfection was defined as cleansing and disinfection of the surface of the facility, endoscopist's isolation gown, and air in the endoscopy room after the examination. Specifically, sanitizing wipes containing quaternary ammonium salt, alcohol, and interfacial activator were used to wipe the surfaces and the air disinfection machine was switched on for 30 min continuously).

Outcomes:**Primary Outcome Measure:**

Qualified rate of room disinfection: The samples of workstation mouse, control panel buttons and patient's bed headboard greater than 10 CFU/cm², samples of endoscopist's isolation gown greater than 200 CFU/100cm², and samples of operation unit air greater than 500 CFU/m³ are deemed as an unacceptable level of bioburden.

The number of colony-forming units (CFU): The number of colony-forming units (CFU) of the sample of operation unit air, workstation mouse, endoscopist's isolation gown, control panel buttons, and patient's bed headboard.

Statistical analysis:

Continuous variables with a non-normal distribution or ordinal variables are expressed as median (the lower four quantiles, the upper four quantiles). Categorized variables are summarized as counts and proportions. Continuous categorical variables were compared using the Wilcoxon signed-rank test (abnormal distribution), whereas categorical variables were compared using the Fisher exact test or chi-squared test.

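### The colony count, a primary outcome, is assigned a paired test (Wilcoxon signed-rank), but the protocol compares two groups and defines no pairs

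*Protocol*

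**What the plan says.** The Statistical analysis section of the protocol names one test for non-normal continuous data: "Continuous categorical variables were compared using the Wilcoxon signed-rank test (abnormal distribution". It continues: "whereas categorical variables were compared using the Fisher exact test or chi-squared test".

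Under Primary Outcome Measure the protocol lists two outcomes. One is the qualified rate, which sets CFU limits for each sampled site. The other is the count itself: "The number of colony-forming units (CFU): The number of colony-forming units (CFU) of the sample of operation unit air, workstation mouse", followed by the three remaining sites.

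The Brief Summary gives the aim as to "evaluate the difference of effectiveness between daily and after-each-case room disinfection in the endoscopy unit". The Detailed Description sets out the comparison: "This study divided into two groups: daily and after-each-case room disinfection groups". It adds: "Each group was again subdivided into sedation and non-sedation gastroscopy, and with or without ventilation operation room". The arms differ in how often the room is disinfected. For the daily arm: "The room disinfection after completing eight non-sedation gastroscopies or four sedation gastroscopies". For the other arm: "The room disinfection performed after completing the examination of each patient".

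**The concern.** The signed-rank test is a one-sample or paired procedure. It needs each daily-arm sample to be tied to one particular after-each-case sample, and the protocol sets out no such tie. The subdivisions by sedation and ventilation create strata, not pairs.

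The protocol also treats the same samples in two ways. A sample counts as qualified or not according to its CFU value. The CFU value goes to a paired test, while the qualified status derived from it goes to Fisher's exact or the chi-squared test, both of which assume independent groups.

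The p-value for a primary outcome is therefore either undefined, if the groups have unequal numbers of samples, or dependent on how an analyst lines the samples up. This is not detail left to a SAP: the protocol names a test, and that test does not fit the design it describes.

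**Working it through.** The protocol gives no sample size, effect, variance or CFU p-value, so there is no figure to reproduce. The check has two parts.

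**1. Test against design**

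- *Which outcome the sentence governs.* It does not name CFU, but CFU is the only continuous outcome listed.
- *What signed-rank needs.* For n pairs, form D_i = X_i − Y_i, rank the |D_i|, and sum the ranks of the positive D_i. Changing which Y goes with which X changes every D_i, and therefore p.
- *What rank-sum needs.* Pool the n₁ + n₂ values, rank them, and take U = R₁ − n₁(n₁ + 1)/2, where R₁ is the rank sum of group 1. No pairing enters, and n₁ and n₂ may differ.
- *What the protocol supplies.* Two groups, strata within them, and five sampled sites. It states no sample numbers, sampling times or matching rule.
- *Could the numbers be unequal?* If sampling followed each disinfection, the same 8 non-sedation cases would give 8 samples per site in one arm and 1 in the other (8:1). For 4 sedation cases the ratio would be 4:1. If sampling followed each case, the numbers could be equal. The protocol does not say which applies. When signed-rank was tried on samples of 8 and 10, the software returned an error.

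**2. Size of the effect (every input assumed)**

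Inputs: independent lognormal CFU, log-SD 1, 16 or 32 samples per group, shift 0 or 0.8 log-SD, two-sided 5% level, 10,000 runs per scenario. The largest simulation standard error is √(0.5 × 0.5 / 10,000) = 0.5 percentage points.

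| | n per group | Rank-sum | Signed-rank, raw CFU | Signed-rank, log CFU |
|---|---|---|---|---|
| Type I error | 16 | 4.5% | 4.2% | – |
| Type I error | 32 | 4.9% | 5.2% | – |
| Power, shift 0.8 | 16 | 55% | 48% | 52% |
| Power, shift 0.8 | 32 | 87% | 82% | 86% |

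The power loss on raw counts is 55 − 48 = 7 points (n = 16) and 87 − 82 = 5 points (n = 32). On log counts it is 3 points and 1 point.

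For dependence on the pairing, data sets were selected by their rank-sum p-value (200 per setting). Each was re-paired at random 2,000 times, and the share of pairings with signed-rank p < 0.05 was recorded.

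| Rank-sum p about | n = 32, raw: median (10th–90th percentile) | n = 32, log: median | n = 16, raw: median |
|---|---|---|---|
| 0.01 | 97% (70–100%) | 100% | 88% |
| 0.03 | 68% (22–94%) | 82% | 50% |
| 0.05 | 35% (7–78%) | 48% | 33% |

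Smaller repeat runs gave the same pattern; they put the 68% entry nearer 60%. In one simulated data set with 16 per group and a rank-sum p of 0.048, re-pairing moved the signed-rank p from 0.003 to 0.298.

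**The case against.** The strongest reply is that the protocol never says the samples are independent. It says only that there are two groups. The same rooms, sites and case positions could have served both regimens, and such matching might be set out in a SAP. If so, the paired test could be right and the Fisher or chi-squared test the misfit.

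The simulation above assumes independence. With an assumed within-pair correlation on the log scale, n = 16 and shift 0.8, the ranking reverses:

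| Correlation | Rank-sum power | Signed-rank power, raw CFU | Rank-sum type I error |
|---|---|---|---|
| 0.3 | 58% | 63% | about 1.7% |
| 0.5 | 60% | 77% | about 1.0% |

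This stands as a caution: rank-sum should not be substituted without first settling whether the samples are matched. It does not rescue the text, because a paired design would make the qualified-rate tests wrong instead.

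A second reply is that this is a wording slip for rank-sum. The contradictory description of the variables as both continuous and categorical makes that plausible. If so, the analysis actually done may be unaffected. The two names still denote different procedures, and an analyst following the text would run the wrong one.

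A third reply is that the harm is small. Type I error holds, the power loss is modest, and unequal groups would produce a visible failure, not a silent bias. That is correct, and it limits the severity.

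**Conclusion.** The concern holds. The only test named for a primary outcome does not fit the design as described, and it conflicts with the tests named for the other primary outcome, which is derived from the same samples. That conclusion rests on the text alone and is firm. It does not establish that the samples are independent; the protocol leaves this open.

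The main consequence is a CFU p-value that is not uniquely defined, or cannot be computed if sample numbers differ. It matters mostly for borderline results: pairing seldom changes the verdict when the rank-sum p is near 0.01, and often does between 0.03 and 0.05. False positives are not inflated if one pairing is fixed in advance. These sizes depend on the assumed distribution, sample numbers and shift, and apply only if the samples are unpaired. In that case the qualified-rate analysis is unaffected. The point should be fixed, but it does not undermine the study.

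**What to change.** State in the Statistical analysis section whether the samples in the two groups are paired, then name matching tests for both outcomes.

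- **If unpaired:** replace the signed-rank test with the Wilcoxon rank-sum (Mann-Whitney) test for between-group CFU comparisons, and keep Fisher's exact or chi-squared for the qualified rate. Cost: one sentence, with no change to data or design.
- **If paired:** define the pairs (for example, same room, surface and case position under both regimens), keep the signed-rank test for that contrast, and use a paired test such as McNemar's for the qualified rate. Cost: one further sentence defining the pairs and a change of test for the qualified rate.

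In either case, correct the description of the variables so that it refers to continuous variables only.

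### CFU counts in two separate groups are assigned a paired test (Wilcoxon signed-rank) with no pairs defined; its unpaired replacement must allow for the daily list if several cases per list are sampled

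*Protocol*

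**What the plan says.** All places are in the Protocol.

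- **Statistical analysis:** "Continuous categorical variables were compared using the Wilcoxon signed-rank test (abnormal distribution), whereas categorical variables were compared using the Fisher exact test", with the chi-squared test as the alternative to Fisher's. No other test is named, and no list, room or day term appears.
- **Detailed Description:** there are two groups, and "Each group was again subdivided into sedation and non-sedation gastroscopy, and with or without ventilation operation room". No matching, crossover or before-and-after sampling is described.
- **Arms and Interventions:** in the daily arm, "The room disinfection after completing eight non-sedation gastroscopies or four sedation gastroscopies"; in the other arm, "The room disinfection performed after completing the examination of each patient". Room disinfection is defined as "cleansing and disinfection of the surface of the facility, endoscopist's isolation gown, and air in the endoscopy room after the examination".
- **Outcomes:** both primary outcomes, the qualified rate and the CFU count, are measured on room air, workstation mouse, gown, control panel and headboard. These are the air, surfaces and gown that room disinfection covers.
- **Eligibility criteria:** "Inclusion Criteria: All the cases received gastroscopy". Eligibility is therefore set by case, but nothing says which cases are sampled or what the unit of analysis is.

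**The concern.** The signed-rank test works on within-pair differences. With two unpaired groups there is no such difference until someone decides which daily sample goes with which after-each-case sample. The protocol gives no rule for that, so the CFU analysis is not defined.

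The obvious repair, a rank-sum test on individual cases, may not be enough. Within a daily list, contamination left by one case can still be present when the next is sampled, because room disinfection comes only at the end. Values from the same list can then be positively correlated. The rank-sum, chi-squared and Fisher tests all take the samples as independent, and the signed-rank test takes the pairs as independent. If each case is entered as its own observation, the information in a list is overstated. At stake are the p-values for CFU and, to a smaller degree, for the qualified rate.

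**Working it through.** The protocol states no sample size, significance level, power or intraclass correlation (ICC), so there is no planned figure to reproduce.

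**Step 1: the paired test.** Eight daily cases can be matched to eight comparator cases in 8! = 40,320 ways, and four to four in 4! = 24 ways. The protocol selects none of these. The defect is that the result is undefined, not that error is inflated: with independent values paired arbitrarily, the signed-rank test rejected in 4.3% to 5.4% of null runs (four settings, 2,000 runs each).

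**Step 2: clustering, by formula.** Inputs are the list size m = 8 or 4 (from the arm definition) and three assumptions: a two-sided 5% level, equal arms, and ICC 0.01 to 0.10. With only the daily arm clustered, the variance of the comparison is multiplied by

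V = 1 + (m − 1) × ICC / 2,

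and the true level is 2 × [1 − Φ(1.96 / √V)]. For m = 8 and ICC 0.10: V = 1 + 7 × 0.10 / 2 = 1.35, √V = 1.162, 1.96 / 1.162 = 1.687, true level 9.2%.

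| ICC (assumed) | m = 8: V | m = 8: true level | m = 4: V | m = 4: true level |
|---|---|---|---|---|
| 0.01 | 1.035 | 5.4% | 1.015 | 5.2% |
| 0.05 | 1.175 | 7.1% | 1.075 | 5.9% |
| 0.10 | 1.350 | 9.2% | 1.150 | 6.8% |

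If the after-each-case arm is equally clustered, V = 1 + (m − 1) × ICC, and m = 8 gives 9.2% and 13.3% at ICC 0.05 and 0.10.

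**Step 3: clustering, by simulation.** The model has a normal latent value, a list random effect in the daily arm only, and 10 lists per arm (assumed), with 6,000 runs (standard error about 0.3 points). Rejection under the null:

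| Test on cases | m = 8, ICC 0.05 | m = 8, ICC 0.10 |
|---|---|---|
| Rank-sum on CFU | 6.7% | 9.2% |
| Chi-squared, 30% unacceptable | 6.3% | 7.6% |
| Chi-squared, 10% unacceptable | 5.4% | 6.1% |
| Fisher, 30% unacceptable | 4.2% | 5.3% |
| Fisher, 10% unacceptable | 3.4% | 3.7% |

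At m = 4 and ICC 0.10: rank-sum 6.4%, chi-squared 6.1%, Fisher 3.4%. The signed-rank test with arbitrary pairing behaves like the rank-sum test: 8.6% at m = 8, ICC 0.10 (2,000 runs). Fisher's starting conservatism (2.9% with no clustering at m = 8) absorbs most of the effect. That protection has limits. At m = 8 and ICC 0.10, Fisher reached 6.2% and 6.4% with 20 and 40 lists per arm, and at ICC 0.30 with 10 lists it reached 10.0%.

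**Step 4: a trend within the list.** The model above treats carry-over as a constant list effect. If CFU also rises with position in the list, that trend adds to the variance a case-level test assumes and works against the inflation. This check used the rank-sum test at m = 8, 10 lists per arm, list effects and the same trend in both arms (assumed), and 4,000 runs:

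| Share of variance due to trend | Residual ICC 0.05 | Residual ICC 0.10 |
|---|---|---|
| none | 9.2% | 13.0% |
| 20% | 5.9% | 9.8% |
| 26% | 4.4% | 7.5% |
| 40% | 2.8% | 4.3% |

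**Step 5: does the repair hold?** An exact unpaired rank test on list means rejected in 3.3% to 5.4% of null runs over all scenarios without trend.

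**The case against.** *The sampling unit is not stated.* A daily list has one room disinfection, and the first primary outcome is a rate of acceptable room disinfection, so one set of samples per list is a natural reading. Sampling each site once per list in both arms, with sites analysed separately, removes the within-list problem. This stands, and it makes the clustering point conditional. A reader might infer that the protocol's p-values are inflated for both primary outcomes. The document does not support that, because it never says that several cases per list are sampled and never gives an ICC.

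*An SAP could settle the unit of analysis.* That is so, and the missing sampling detail is not itself the defect. But the protocol commits to a named test that does not fit its two-group design, and that can be judged from the text as it stands.

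*Signed-rank may be a slip for rank-sum.* Possibly; the text does not tell. The correction is the same either way.

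*Clustering in one arm under a true null is an awkward scenario.* If disinfection removes carry-over, the arms probably differ and the null is false; if it does nothing, both arms carry over. This is fair: the one-arm figures are an illustration. In the first case the harm is overstated precision rather than false positives. In the second the two-arm figures (9.2% and 13.3%) apply.

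*Inflation is not assured.* This also stands. A strong trend with position can cancel it, and Fisher's test shows almost none at ICC up to 0.10 with 10 lists per arm.

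**Conclusion.** Firm: the signed-rank test is wrong as written for CFU in two separate groups with no pairs defined. This rests on the text alone and needs no assumption.

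Conditional: if more than one case per daily list is sampled and analysed as a separate observation, swapping in a case-level unpaired test can still leave p-values too small. For CFU the true level is about 7% to 9% at m = 8 and 6% to 7% at m = 4, given an assumed ICC of 0.05 to 0.10 and clustering in the daily arm only. It is negligible at ICC 0.01, about nil for Fisher in most of these settings, intermediate for chi-squared, and possibly absent if CFU trends strongly over the list. That all cases of a list share one room is implied by the arm definition rather than stated.

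How to allow for testing five sampling sites is a separate matter and no part of this point.

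**What to change.** 1. Replace the signed-rank test with an unpaired comparison of the two arms at each site: a rank-sum or permutation test stratified by sedation and ventilation. Correct the description of the variables it applies to, since continuous and categorical exclude each other.
2. Record a room-list identifier on each sample. In the after-each-case arm, a block of consecutive cases in the same room can serve as the counterpart.
3. State which cases are sampled. If several per list, compare arms by site on list-level summaries (proportion acceptable, mean log CFU with a stated rule for zero counts), or use a mixed model or GEE with a list effect and a small-sample correction.
4. Combine the sedation and ventilation subgroups by stratification rather than testing within each.

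**Cost.** Wording and one field on the sampling form; the intervention does not change. At m = 8 with only the daily arm clustered, intervals widen by √1.175 = 1.08 to √1.35 = 1.16. If there is no clustering, power falls from 78% to 72% (simulated, 10 lists of 8 per arm, latent shift 0.45 SD). Few lists limit resolution: the smallest two-sided exact rank p-value with L lists per arm is 2 / C(2L, L), which is 2/20 = 0.10 for L = 3, 2/70 = 0.029 for L = 4 and 2/252 = 0.008 for L = 5. Separate tests inside the subgroups could therefore be uninformative, which is the reason for item 4.
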